Evaluation of a Computerized Intervention for Learning to Re-Evaluate Suicidal Thoughts

NCT04254809

[Date: 4/27/2021]

Background.

As rates of suicide have increased over the last several decades, research has identified that roughly two-thirds of individuals who attempt suicide do so within one year from the time that they begin to think about suicide. This suggests a greater need for interventions designed to specifically help individuals learn to cope with thoughts of suicide to interrupt the process by which thoughts may lead to suicidal behaviors (i.e., attempts). It is common that individuals with suicidal ideation may not understand where thoughts of suicide come from and are therefore distressed at the prospect they might never escape these thoughts. As a result, these individuals may attempt to distract from or avoid these thoughts in ways that contribute to suicidal ideation becoming more frequent and intense over the long-term. This 'experiential avoidance' of suicidal ideation is therefore an excellent target for treatment and has in fact been shown to help reduce the distress associated with suicidal thoughts in several treatment studies.

The intervention to be tested in this study seeks to reduce the distress related to suicidal thoughts by explaining that these thoughts are a normative response to extreme stress, and provides strategies that help individuals observe that suicidal thoughts are temporary (i.e., will not last "forever") and something they can tolerate without needing to rigidly control them. To maximize the potential of this intervention to help the largest number of individuals, it is entirely computerized and takes only 30 minutes to complete. This will help reduce many of the traditional barriers to treatment that individuals with suicidal ideation face (e.g., costs, time restrictions, and stigma of help-seeking).

Objectives.

Individuals (N=106) with current suicidal ideation will be randomly assigned to participate in either the experiential avoidance intervention for suicidal thoughts or a control intervention. Experiential avoidance (i.e., distress or avoidance) and severity of suicide risk will be measured one week, and one month after participants complete their assigned intervention. It is hypothesized that, compared to controls, individuals who receive the experiential avoidance intervention will report: 1) less experiential avoidance at one week follow-up, and 2) less severe suicide risk at one-month follow-up.

Design.

This is a double-blinded randomized treatment trial with two-arms (active and control conditions).

Power Analysis.

An a priori power analysis was conducted. Expected effect size was estimated given the reported effect of a similar single-session computerized intervention in a prior study. Compared to a health intervention control, Schmidt, Norr, Allan, Raines, and Capron (2017) reported a small-sized effect ($f = .18$) of a brief computerized intervention for Anxiety Sensitivity on pre-intervention to one-month change in BSS suicidal ideation scores among participants (N = 72) with current suicidal ideation. Like REST, the active intervention described in that study was delivered by computer, sought to de-catastrophize cognitive symptoms of mental dyscontrol and anxiety, and led participants through exercises to demonstrate a sense of control over mental and physical symptoms of anxiety. Projecting a similar small-sized ($f = .18$) main effect of REST on BSS suicidal ideation at one-month follow-up, estimating power to be 80%, and using an alpha value of .05, a two-group a priori repeated measures (i.e., pre-intervention and one-month follow-up) power analysis conducted in G*Power (version 3.1.9.2) suggested a sample size of 88. To further account for a 20% attrition rate at one-month follow-up, 106 participants were anticipated to be recruited for this study.

Methods.

At the baseline appointment participants provided written informed consent to participate in the study. Next, they completed a battery of self-report measures including the AAQ-SI, WBSI-SI, and BSS. Next, participants completed their assigned intervention condition from a desktop computer in a private room. Participants were assigned to intervention condition according to a random numbers table that was created prior to participant recruitment. Following the intervention all participants completed the AAQ-SI. Participants then spent two minutes writing about their recent suicidal thoughts, followed by a five-minute thought monitoring period, after which they completed the WBSI-SI to measure avoidance of suicidal ideation during the thought monitoring period. Lastly, a graduate-level clinician collaborated with participants to generate a safety plan for mitigating risk of future suicide attempt. Participants were then debriefed on the day's appointment, scheduled for their one-week follow-up check-in, and compensated (\$20 or two research credits) for participation.

At the one-week follow-up appointment participants were sent an email containing a web-link to complete a battery of self-report follow-up questionnaires including the AAQ-SI, WBSI-SI, and BSS via Qualtrics. Completion of this survey triggered an email alert to study personnel, after which a suicide risk check-in was conducted over the telephone with a graduate-level clinician. Clinicians also helped participants update their individual safety plans as needed. Participants were then reminded of the date for their one-month follow-up check, and confirmed compensation for that appointment (\$5 Amazon gift card or 0.5 research credits). These same procedures were followed for the one-month follow-up appointment, with the addition of debriefing following the one-month appointment. All participants in the control condition were offered the opportunity to complete the REST intervention following their last follow-up appointment. All procedures were approved by the Florida State University Institutional Review Board.

Statistical Analysis Plan.

Power Analysis. An a priori power analysis was conducted. Expected effect size was estimated given the reported effect of a similar single-session computerized intervention in a prior study. Compared to a health intervention control, Schmidt, Norr, Allan, Raines, and Capron (2017) reported a small-sized effect ($f = .18$) of a brief computerized intervention for Anxiety Sensitivity on pre-intervention to one-month change in BSS suicidal ideation scores among participants ($N = 72$) with current suicidal ideation. Like REST, the active intervention described in that study was delivered by computer, sought to de-catastrophize cognitive symptoms of mental dyscontrol and anxiety, and led participants through exercises to demonstrate a sense of control over mental and physical symptoms of anxiety. Projecting a similar small-sized ($f = .18$) main effect of REST on BSS suicidal ideation at one-month follow-up, estimating power to be 80%, and using an alpha value of .05, a two-group a priori repeated measures (i.e., pre-intervention and one-month follow-up) power analysis conducted in G*Power (version 3.1.9.2) suggested a sample size of 88. To further account for a 20% attrition rate at one-month follow-up, 106 participants were anticipated to be recruited for this study.

Equivalence of Random assignment. Equivalence of random assignment to condition was evaluated with independent sample t-tests for continuous variables and chi-square tests of independence for categorical variables. There were no significant differences observed between intervention conditions for any demographic variables (e.g., age, sex, race; all p 's > .622) or psychological variables at baseline (e.g., AAQ-SI, WBSI-SI, BSS; all p 's > .210)

Missing Data. All variables were evaluated for missing data at each study time point. No missing values were identified at the baseline, post-intervention, or thought monitoring time-points. At one-week follow-up there were four values (4.2% of cases) missing. At one-month

follow-up there were 20 values missing (20.8% of cases). Little's test for data MCAR was non-significant ($\chi^2[38] = 48.42, p = .120$), suggesting that values were indeed MCAR. The a priori plan for handling longitudinal missing data, assuming data MCAR and equivalence of random assignment, was to replace missing values with the last-observation-carried-forward method.

Differences among completer samples. Baseline differences were evaluated among individuals who complete the one-month follow-up (i.e., completers) and those who were lost-to-follow-up (i.e., non-completers). Equivalence of random assignment to condition was evaluated with independent sample t-tests for continuous variables and chi-square tests of independence for categorical variables. There were no differences among those who provided complete data versus those who were lost to follow-up on any demographic variables (all $p > .511$) or baseline psychological variables (all p 's $> .249$). Similarly, there were no significant differences between conditions with respect to completer status, $\chi^2(1) = 1.64, p = .200$.

Assumptions of Normality. All self-report outcome variables were assessed for skewness, kurtosis, and outliers. Outliers were hand-corrected utilizing the interquartile range (IQR), to fall at the value $1.5 \times \text{IQR} \pm Q3/Q1$. No AAQ-SI data were corrected. Five low-lying outliers were corrected to $Q1 - 1.5 \times \text{IQR}$ for the WBSI-SI. One high value was corrected to $Q3 + 1.5 \times \text{IQR}$ for the BSS. After correction, all values evidenced acceptable skew and kurtosis values of $< |2|$.

Change scores. Standardized residualized change scores were calculated for all outcome variables by regressing scores of each measure at the follow-up time point (i.e., one-week for AAQ-SI and WBSI-SI, and one-month for BSS) onto scores of their respective baseline measure.

Primary Analyses. All analyses were conducted in SPSS Version 26. To examine the first primary outcome, the direct effect of condition on change in distress of suicidal ideation at one-week, a linear regression model was conducted with condition as the independent variable and standardized residualized change in AAQ-SI the dependent variable. To examine the second primary outcome, the direct effect of condition on change in suicidal ideation severity one-month, a linear regression model was conducted with condition as the independent variable and standardized residualized change in BSS the dependent variable.

Secondary Analyses. To examine the first secondary outcome, the direct effect of condition on change in avoidance of suicidal ideation at one-week, a linear regression model was conducted with condition as the independent variable and standardized residualized change in WBSI-SI the dependent variable.

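### Read literally, carry-forward would fill a missing one-week WBSI-SI with a score about a five-minute task; the plan should bar that reading and name the one carried (minor)

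*Combined protocol and SAP*

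**What the plan says.** The Methods section gives three occasions up to one week for each of the two scales.

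- **Before the intervention.** "Next, they completed a battery of self-report measures including the AAQ-SI, WBSI-SI, and BSS".
- **Same day, after the intervention.** For the AAQ-SI: "Following the intervention all participants completed the AAQ-SI". The WBSI-SI comes later that day, after two minutes of writing about recent suicidal thoughts and five minutes of thought monitoring: "after which they completed the WBSI-SI to measure avoidance of suicidal ideation during the thought monitoring period".
- **One week.** Both scales are part of an online follow-up battery. No writing or monitoring task is described there.

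The Missing Data section reports that the same-day readings are complete: "No missing values were identified at the baseline, post-intervention, or thought monitoring time-points". It then reports the one-week gap: "At one-week follow-up there were four values (4.2% of cases) missing". The a priori plan for longitudinal missing data "was to replace missing values with the last-observation-carried-forward method". No sentence says which earlier reading is the one carried.

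The Change scores section regresses each follow-up score on its own baseline measure, at these time points: "i.e., one-week for AAQ-SI and WBSI-SI, and one-month for BSS". One-week AAQ-SI change is the first primary outcome (Primary Analyses). One-week WBSI-SI change is the first secondary outcome (Secondary Analyses).

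**The concern.** Carry-forward needs the earlier reading to measure the same thing as the missing one. For the WBSI-SI, the plan's own description limits the same-day reading to an induced task lasting minutes. If that score stands in for a one-week score, the secondary outcome mixes avoidance during a laboratory exercise with avoidance reported at follow-up, and the mixture is then regressed on an ordinary pre-intervention questionnaire score. This would be a fault even if the missing values were missing completely at random (MCAR).

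For the AAQ-SI the issue is milder. A reading from straight after the session would count as a one-week score, in a primary outcome meant to show whether a change is present a week later.

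At stake are the content of up to four one-week values per scale and whether a reader can tell how they were filled.

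**Working it through.** **1. The plan's own figures.** One month: "follow-up there were 20 values missing (20.8% of cases"). Of the sample sizes from 60 to 129, only n = 96 gives 20/n = 20.8%. At one week, 4/96 = 4.17%, which rounds to the stated 4.2%. The two figures agree on 96 cases. If the four values are four participants with no one-week data, four scores are missing on each scale. If they are single scale scores, fewer are missing on each. Four per scale is therefore the upper limit, leaving 96 − 4 = 92 observed.

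**2. Which reading is last.** No same-day values are missing, so every missing one-week score has a same-day predecessor on the same scale.

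| Scale | Last reading before one week | What it refers to | Outcome |
|---|---|---|---|
| WBSI-SI | After writing and thought monitoring, same day | The five-minute monitoring period | First secondary |
| AAQ-SI | Straight after the session, same day | No changed wording or reference period stated | First primary |

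The BSS is not touched by this point: no same-day BSS after the intervention is described.

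**3. Possible size.** Two inputs are assumed because the documents do not give them.

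- Arm sizes: 96/2 = 48 per arm.
- Gap g: carried score minus the one-week score that would have been observed, in SDs of the analysed change score. The baseline regression slope is held fixed.

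With a replaced values in one arm, b in the other and the same gap for all:

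shift in arm difference = g × (a − b) / 48

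| Split | g = 0.5 SD | g = 1 SD |
|---|---|---|
| 2:2 | 0 | 0 |
| 3:1 | 0.5 × 2/48 = 0.02 | 1 × 2/48 = 0.04 |
| 4:0 | 0.5 × 4/48 = 0.04 | 1 × 4/48 = 0.08 |

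If missingness is unrelated to arm, the chance that all four fall in the same arm is 2 × C(48,4)/C(96,4) = 2 × 194,580/3,321,960 = about 12%.

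Gaps need not be equal across arms. With a 2:2 split and a 1 SD gap in one arm only, the shift is 2/48 = 0.04 SD. With 1 SD gaps in opposite directions it is 4/48 = 0.08 SD. An extreme 2 SD gap, with all four in one arm or in opposite directions across arms, gives 8/48 = 0.17 SD.

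**4. Yardstick.** The standard error of the arm difference with SD = 1 is √(2/48) = 0.20 SD. A shift of 0.08 SD is about 0.4 of a standard error (0.083/0.204 = 0.41). The assumed effect f = .18 in the Power Analysis is not a fair comparator, because it was set for the BSS at one month and no expected effect is given for either one-week scale.

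**The case against.** **The AAQ-SI reading is not a different quantity.** A reader might infer that a primary outcome is filled with something other than what it claims to measure. The documents do not support that. They describe the same scale, with no altered wording, task or reference period, taken about a week early. Assuming that an earlier level persists is the ordinary weakness of carry-forward. This objection stands, and the mismatch of content is limited to the WBSI-SI.

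**No wrong entry is shown.** A reader might infer that wrong values went into the analysis. The plan never says which reading was carried, and the change scores use only baseline and follow-up, so the sponsor may have carried the pre-intervention score. This also stands. But that score is not the last observation when a complete same-day reading exists, so the plan needs a sentence either way.

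**No direction of bias is established.** It is tempting to say that a session effect is largest on the day, so that carry-forward flatters the intervention. The documents give no time course for either scale, so neither direction nor size can be claimed.

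**The remedy departs from an a priori rule.** Carry-forward was planned, and the text already reports the missing data in the past tense, so a change now is post hoc and drops up to four randomised participants. This stands in part. It is a reason to keep carry-forward visible as a sensitivity analysis and to label the change openly. It is not a reason to keep a task-specific score in a one-week outcome, since under the MCAR assumption on which the plan itself relies, leaving the missing cases out adds no bias.

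**Conclusion.** The point holds for the WBSI-SI: the rule as written would put a score about a five-minute task into up to 4 of 96 values of the first secondary outcome. For the AAQ-SI, all that can be said is that the literal rule assumes the level straight after the session lasts a week. For both scales the source reading is unnamed, and what was actually carried is unknown.

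Severity is minor. For common gaps of up to 1 SD and 48 per arm, both assumed, the arm difference shifts by 0 to 0.08 SD against a standard error of about 0.20 SD. The upper end needs all four values in one arm. Such a shift could matter for a borderline result but would not normally change a conclusion. The case for acting is that the repair is cheap, not that the bias is large. The statement that observed-case analysis adds no bias depends on MCAR, which the plan assumes.

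**What to change.** In Missing Data:

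- State that the thought-monitoring WBSI-SI may not replace a one-week value.
- Analyse the observed one-week scores (about 92 of 96) for the WBSI-SI and AAQ-SI.
- Show the carry-forward result as a sensitivity analysis, naming for each scale the reading that was carried.
- Record that the change was made after the extent of missing data was known.

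The cost is a few sentences and a rerun of two regressions. The downside is at most four fewer cases per outcome. The one-week scales would also follow a different missing-data rule from the one-month BSS, unless the plan changes that rule too.

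### The recruitment target of 106 keeps the required 88 only up to about 17% attrition, not the stated 20%, which would have needed 110

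*Combined protocol and SAP*

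**What the plan says.** The combined protocol and SAP prints one Power Analysis paragraph twice: as its own section before Methods, and as the first item of the Statistical Analysis Plan. The arguments are the same in both: an effect size of f = .18 on the BSS, a two-group design with two measurements (before the intervention and at one month), and "estimating power to be 80%, and using an alpha value of .05". The calculation "suggested a sample size of 88". The next sentence sets the recruitment target: "To further account for a 20% attrition rate at one-month follow-up, 106 participants were anticipated to be recruited for this study".

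The Objectives section uses the same figure as the number to be randomised: "Individuals (N=106) with current suicidal ideation will be randomly assigned".

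Neither copy of the paragraph shows how 88 became 106. No section says that the 20% is a share of anything other than the participants recruited. The Missing Data section adds that the prior plan for missing follow-up values "was to replace missing values with the last-observation-carried-forward method".

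**The concern.** An allowance for attrition has one job: after the assumed share of recruits is lost, the number that the power calculation asked for should still be there. Here the required number, the assumed rate and the target are all stated, so the claim can be checked directly, and 106 is too small for 88 and 20%.

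What is at stake is the accuracy of the design record. The one-month BSS is the outcome on which the trial was sized, and it is the second primary outcome in the Primary Analyses section. A reader would take the design to tolerate 20% loss at that visit with 88 observed values intact, when it tolerates 17.0%. Someone planning a similar trial could also copy the method of inflation, whose error grows with the dropout rate.

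**Working it through.** **Inputs, all from the Power Analysis paragraph (both copies)**

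- Required number: n = 88
- Assumed attrition at one month: d = 0.20
- Stated recruitment target: N = 106 (also in Objectives)

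**Step 1. Reproduce the stated figure.** Adding the allowance to the required number, n × (1 + d):

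88 × 1.20 = 105.6, rounded up to 106.

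This matches exactly. The document gives no formula, so it shows how 106 probably arose, not how it is known to have arisen.

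**Step 2. Target that keeps 88 after 20% loss.** Solve N × (1 − d) = n, so N = n / (1 − d):

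88 / 0.80 = 110.0.

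One fewer does not suffice: 109 × 0.80 = 87.2.

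**Step 3. What 106 delivers at 20% loss.**

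106 × 0.80 = 84.8. In whole participants, 0.20 × 106 = 21.2, and 21 losses leave 85.

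**Step 4. Attrition that 106 covers.**

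106 − 88 = 18 losses; 18/106 = 16.98%, that is 17.0%. A nineteenth loss (19/106 = 17.9%) leaves 87.

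**Summary**

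| Recruited | Losses that still leave 88 | Attrition covered | Left at 20% loss |
|---|---|---|---|
| 106 (as stated) | 18 | 17.0% | about 85 |
| 110 (from 88/0.80) | 22 | 20.0% | 88 |

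The shortfall is 110 − 106 = 4 recruits, or 88 − 85 = 3 observed one-month values. Rounding does not explain it, since 88/0.80 is a whole number.

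**The case against.** The best defence is that the sentence never promises that 88 will remain. It says that 106 allows for 20% attrition, and a 20% addition to 88 does give 106. As an account of what was done, that is plausible. As a reading of the sentence, it is the less natural one: attrition at a follow-up visit is lost from those who entered, and the Missing Data section itself reports missing values as a percentage of cases. Nothing in the document defines the 20% as a share of 88.

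It is also fair to say that the practical effect is close to nil. The document already reports baseline comparisons, missing data and completer results, so recruitment can no longer change. The two sections repeat one paragraph, so this is one slip and not two. Both points stand, and they are why the point is minor.

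Three stronger readings are tempting, and the document supports none of them.

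- *That the trial was therefore powered below 80%.* This needs the test and the correlation entered in G*Power, and neither is stated. Taking f = .18 and alpha .05, a within-between interaction gives 88 only if the correlation between the two measurements is assumed to be about 0.29 to 0.30. The text speaks of a main effect, and a between-group main effect would need 124 even at a correlation of 0. The planned test is a regression of residualised change on condition, with missing values carried forward, so a power figure for observed values would not describe the planned analysis.
- *That the reported one-month loss shows harm from the slip.* The Missing Data section gives 20 missing values (20.8%), and the percentages imply 96 cases, so 76 were observed. At that rate 106 would leave 106 × 76/96 = 83.9, but 110 would leave 110 × 76/96 = 87.1, which is also below 88. The reported loss exceeded the 20% assumption itself, so it does not separate the two targets.
- *That carrying the last observation forward removes the issue because everyone randomised is analysed.* The plan says how missing values are replaced. It defines no analysis population and does not report how many were randomised (106 planned, about 96 cases implied). In any case, the method would not make the attrition sentence correct.

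**Conclusion.** The attrition statement is wrong as written, and the error is minor. Given 88 and 20%, the target is 110; 106 covers 17.0%, and at 20% loss it leaves about 85 observed one-month values. The size is 4 recruits, or about 3 observed values.

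The conclusion takes 88 as given and rests on one reading: that 20% attrition means a fifth of those recruited. It does not depend on which test was run in G*Power. That 106 came from multiplying by 1.2 is an inference from an exact match. Nothing here bears on the planned analyses or on any result in the document, and no claim about the power achieved follows from it.

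**What to change.** Keep 106 as the target on record, including in Objectives, and reword the attrition sentence in both copies of the Power Analysis paragraph. Suggested text:

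> The recruitment target was 106. From a required 88, this allows for up to 18 losses, or about 17% attrition at one month. Retaining 88 at 20% attrition would have needed 110 (88/0.80); with 106, about 85 observed one-month values would remain at 20% loss.

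Add no recalculated power figure and no statement about who remains in the analysis, since the document supports neither. The cost is a short rewording in two places, with no further enrolment and no re-analysis.

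### A non-significant Little's test is read as support for MCAR, but it has low power here and cannot see loss tied to the unseen one-month BSS; no sensitivity analysis covers this for the second primary outcome

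*Combined protocol and SAP*

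**What the plan says.** All of this is in the Statistical Analysis Plan.

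- **Missing Data, extent.** "At one-week follow-up there were four values (4.2% of cases) missing". At one month 20 values were missing, given as 20.8% of cases.
- **Missing Data, inference.** Little's test is reported as non-significant (chi-square 48.42 on 38 df, p = .120), "suggesting that values were indeed MCAR".
- **Missing Data, handling.** The a priori rule, "assuming data MCAR and equivalence of random assignment, was to replace missing values with the last-observation-carried-forward method".
- **Differences among completer samples.** "There were no differences among those who provided complete data versus those who were lost to follow-up on any demographic variables" (all p > .511), nor on baseline psychological variables (all p > .249). Completer status did not differ significantly by condition (chi-square 1.64 on 1 df, p = .200). Counts per arm are not given.
- **Primary Analyses.** For the second primary outcome, "a linear regression model was conducted with condition as the independent variable and standardized residualized change in BSS the dependent variable".

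Neither the protocol text nor the SAP describes multiple imputation, a likelihood-based model, a shift analysis or any other sensitivity analysis for missing BSS values.

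**The concern.** Failing to reject a null hypothesis is not evidence that it is true, least of all when the test is weak. Little's test compares the means of observed variables across missingness patterns. The question for the one-month BSS is whether participants who did not return were doing better or worse at one month than their earlier scores suggest. The test reaches that question only through the correlation between observed scores and the missing one.

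In a trial of suicidal ideation it is plausible that return at one month depends on how the participant is doing then. If that dependence differs by condition, the second primary contrast is biased. About a fifth of the one-month values are missing, and no planned analysis shows how far the conclusion depends on what is assumed about them.

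**Working it through.** **1. The plan's own figures.** The upper tail of chi-square(38) at 48.42 is .1199, which matches .120. The percentages imply N = 96: 20/96 = 20.8% and 4/96 = 4.2%. That leaves 76 with one-month values.

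**2. Power against a shift in observed variables.** Let D be the standardised difference between the 20 lost and the 76 retained, with all of the departure in that contrast (assumption). The noncentrality is λ = D² × 76 × 20/96 = 15.83 D². The critical value of chi-square(38) at alpha .05 (assumed) is 53.38.

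| D (SD) | λ | Power |
|---|---|---|
| 0.3 | 1.43 | 7% |
| 0.5 | 3.96 | 12% |
| 0.8 | 10.13 | 29% |
| 1.0 | 15.83 | 49% |
| 1.2 | 22.80 | 70% |

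Reaching 80% power takes about 1.3 SD.

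**3. Power when loss depends on the unseen BSS.** The observed shift is then D = r × (unseen shift), where r is the correlation of the observed variables with the unseen score. The documents do not give r, so it is taken as 0 to 0.7. Power is 5–8% for an unseen shift of 0.5 SD, 5–14% for 0.8 SD and 5–22% for 1.0 SD.

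A simulated Little's test (400 runs per setting, a variable set assumed so that df = 38) agrees. It rejected in 5.5% of runs under MCAR, in 10% and 24% for observed shifts of 0.5 and 0.86 SD, and in 4.5% and 13% for unseen shifts of 0.47 and 0.86 SD.

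**4. What p = .120 leaves open.** The statistic exceeds its df by 48.42 − 38 = 10.42. Placed wholly in the one-month contrast, that is √(10.42/15.83) = 0.81 SD, with a 97.5% upper bound of about 1.5 SD. The result is compatible with no shift and with a large one.

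**5. Effect on the BSS contrast.** Simulation assumptions: 48 per arm, 10 losses per arm, correlation .6 between baseline, one-week and one-month BSS, lost participants carrying their one-week score forward, and no true effect.

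| Loss mechanism (odds ratio 2 to 3 per SD of unseen BSS) | Planned LOCF | Observed cases only |
|---|---|---|
| REST arm only | .04 to .07 raw SD in REST's favour | .09 to .14 raw SD in REST's favour |
| Both arms alike | near zero | near zero |

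To set the LOCF figure against a standard error: the residual SD given baseline is √(1 − .6²) = .8, so .04 to .07 raw SD is .05 to .09 residual SD. The standard error is about 2/√96 = .204 residual SD, so the bias is about a quarter to just over two-fifths of it.

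A hand check: if the values assigned to one arm's missing participants are wrong by 0.5 SD, the contrast moves by .208 × 0.5 = .10 SD, or .25 × 0.5 = .125 SD at 25% loss. The planned effect is d = 2 × .18 = .36 if f is read as a two-group f.

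**6. Counts by arm.** For 20 missing among 96, with arm sizes from 36/60 to 48/48, no split was found that gives 1.64. At 48 per arm the nearest splits are:

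- 7 v 13: 96 × (7×35 − 13×41)² / (48×48×20×76) = 2.27
- 8 v 12: 96 × (8×36 − 12×40)² / (48×48×20×76) = 1.01

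Nineteen non-completers split 7/48 v 12/48 do match: 96 × (7×36 − 12×41)² / (48×48×19×77) = 1.64. Loss would then be 14.6% v 25%.

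**The case against.** The best defence has four parts.

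- **LOCF was fixed in advance.** The test did not select the method. That is right. But the rule is stated as assuming MCAR, and the test is offered in support of that premise.
- **The plan did not rely on Little's test alone.** It also compared completers with non-completers, and loss by condition. These checks deserve credit, but they cover baseline variables and the number lost. Neither reaches how lost participants were doing at one month.
- **The harm needs asymmetry between arms.** This stands. When both arms lose participants alike, with equal numbers lost, the simulated bias is near zero.
- **The power figures depend on assumptions.** This also stands, because the SAP does not list the variables in the test.

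A reader might infer more than the documents support:

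- That the test has almost no power. That fits small shifts and loss driven mainly by the unseen score, but not a 1.0 SD observed shift, where power is 49%.
- That the plan rules out informative loss. Its wording is only that the test suggests MCAR, and it makes no claim about informative loss differing by arm.
- That the larger observed-case bias applies to the primary result. The plan does not run an observed-case analysis; under LOCF the bias is about half as large.

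**Conclusion.** The point holds as a modest one. A low-powered, non-significant test is given more weight than it can bear, and the second primary outcome, with 20.8% missing, has no analysis of what follows if the MCAR premise fails. Nothing in the documents shows that loss was informative or that the BSS result is biased.

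Under a deliberately one-sided mechanism, the planned contrast would move by about .04 to .07 raw SD towards REST. That is small beside a planned effect of about .36, but enough to matter for a result close to significance. The figure rests on the assumed odds ratios, the .6 correlations, 10 losses per arm and carrying forward the one-week score.

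MCAR would not justify LOCF in any case, because LOCF also needs scores to stay unchanged after the last observation. For the same reason it would be wrong to describe the LOCF analysis as resting on missing at random.

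The mismatch between 20 missing values and the completer chi-square is a matter for reconciliation, not proof of error. A missing value and a non-completer may have been counted differently, and arm sizes are not stated.

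**What to change.** 1. In Missing Data, replace the clause "suggesting that values were indeed MCAR" with a statement that the test does not establish MCAR, and that LOCF additionally assumes no change after the last observed score.
2. Add one sensitivity analysis for one-month BSS. Impute the missing values by multiple imputation from condition, baseline and one-week scores (missing at random), and apply the planned regression to each imputed data set. Repeat with the imputed values shifted upward by 0 to 1 SD, in REST only and then in both arms. Report the shift, if any, at which the conclusion changes. The both-arms version matters if loss was unequal: at 7/48 v 12/48, a 0.5 SD shift in both arms moves the contrast by (12 − 7)/48 × 0.5 = .05 SD.
3. Report missing counts by arm at each follow-up, and reconcile them with the completer chi-square of 1.64.

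The cost is a reworded paragraph, a small table of counts and one extra analysis on data already held. The downside is that a positive BSS result may have to be described as less robust.
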